## Step 5: combine the estimates for the 100 datasets into I PE, and use mianalyze in order to give 1 p-value for the treatment comparison corresponding to each delta value fitted.

```
PROC MIANALYZE DATA= i_PE;
   MODELEFFECTS estimate;
   STDERR stderr;
   ODS OUTPUT PARAMETERESTIMATES = i_output&i.;
RUN;
```

CONFIDENTIAL Page 121 of 139

# **Secondary Endpoint: Status for exacerbation free over the 52-week treatment period**

```
PROC LOGISTIC DATA=<dataIn>;
  CLASS trtn(REF='3')
       region1(REF='North America')
        numpes (REF='>=3')
       psaecol(REF='Negative')
        agegr3(REF='Adult');
 MODEL statusn(EVENT='1') = trtp region1 numpes psaecol agegr3 /
    CLODDS=WALD ORPVALUE;
  ODDSRATIO "COMPARISON" trtp / DIFF=ALL CL=WALD ;
  ODS OUTPUT ODDSRATIOSWALD=<dataOut> MODELANOVA=<dataOut>;
RUN;
              participants treatment (brensocatib 25mg, brensocatib 10mg,
 trtp
               stratification factor: North America, Europe, Japan, and
region1
               the Rest of the World
               stratification factor: sputum sample being classified as
 psaecol
               positive or negative for Pseudomonas aeruginosa at
              screening visit
              stratification factor: number of prior PEs [<3 or ≥3] in
numpes
              the previous 12 months
statusn status variable with 1=responder and 2=non-responder agegr3 age group: adult, adolescent
```

# Secondary Endpoint: imputation of missing event times for participants who discontinued early without an exacerbation

### **Step 1:** Create a dataset named tte containing 1 row per participant and the following variables

```
usubjid participants identifier

trtp participants treatment (brensocatib 25mg, brensocatib 10mg, placebo)

region1 stratification factor: North America, Europe, Japan, and the Rest of the World

psaecol stratification factor: sputum sample being classified as positive or negative for Pseudomonas aeruginosa at screening visit

numpes stratification factor: number of prior PEs [<3 or ≥3] in the previous 12 months

trtp participants treatment (brensocatib 25mg, brensocatib 10mg, placebo)

ttpe Time to first pulmonary exacerbation event
cnsr Censoring flag (1=censored, 0=event);
```

Note: Participants who discontinued the study early without a PE will be censored at the time of discontinuation for implementation of Step 3 below.

CONFIDENTIAL Page 122 of 139

# Step 2: Fit a bayesian piecewise exponential model using the default of 8 intervals – assuming piecewise constant hazards and a gamma prior outputting the survival estimates for each set of covariates into pred1 dataset.

The below estimates the survival function  $\hat{S} = (c_i | x_i, \hat{\beta})$  where  $c_i$  is the censoring time of participant  $i, x_i$  is a vector of participants covariate values observed at or prior to initiation of study treatment, and  $\hat{\beta}$  is a vector of model parameters samples from a posterior Bayesian distribution of model parameters estimated from the observed data.

### **Step 3:** Merge the survival function estimates for each set of covariates back onto the tte input dataset, following steps b.1 to b.3 below.

- (b.1) Compute  $p_i = 1 \hat{S}(c_i|x_i, \hat{\beta})$
- (b.2) Draw a uniform random value  $u_i \sim \text{uniform}[p_i, 1]$
- (b.3) Impute the event time  $t_i^*$  as the solution of  $u_i = 1 \hat{S}(t|x_i, \hat{\beta})$ . This will ensure that the imputed event time will be greater than the censoring time (and in fact the imputed time will be sampled from the conditional survival  $\hat{S}(t|t > c_i, x_i, \hat{\beta})$ ).
- (b.2) will be repeated 100 times creating 100 separate datasets each of which will be used to estimate the event times per participant as follows:

```
*--- merging survival estimate back to original dataset ---;

PROC SQL;

CREATE TABLE tte2 AS

SELECT pred1.survival,

tte.trtn, tte. Region1, tte.psaecol,

tte.numpes, tte.agegr3, tte.ttpe, tte.usubjid, tte.cnsr

FROM tte LEFT JOIN pred1

ON pred1.trtn =tte.trtn AND pred1.region1 =tte.region1 AND

pred1.psaecol =tte.psaecol AND pred1.numpes=tte.numpes AND

pred1.agegr3=tte.agegr3 AND

pred1.ttpe =tte.ttpe;

QUIT;
```

CONFIDENTIAL Page 123 of 139

```
*--- ensuring survival estimate presents for all rows ---;
DATA tte3 (DROP=survival);
 SET tte2;
 BY trtn region1 psaecol numpes agegr3;
 RETAIN o surv;
 IF FIRST.numpes THEN o surv=.;
 IF survival ne . THEN o surv=survival;
 ELSE IF survival =. THEN survival=o surv;
RUN;
*--- Compute failure function p=1-survival curve (separate curves for
      each set of covariates) ---;
*--- Draw a uniform random value constrained to be >p and < 1 ---;
*--- use 100 different seeds to ensure reproducibility ---;
DATA createSeed;
 CALL STREAMINIT (351985287);
 DO i=1 TO 100;
    seed=1000 + INT(RAND("UNIFORM")*10000000);
   OUTPUT;
 END;
RUN;
DATA tte4 (RENAME=ttpe =o_ttpe);
 SET tte3;
 call streaminit(<SEED from above dataset>);
 p=1-(o surv);
 u=RAND('uniform',p,1); *new failure rate*;
 n surv=1-u; *new survival rate*;
RUN;
*--sort by descending n surv and keep only rows with subjid present ---;
proc sort data=tte4 (keep=usubjid n surv trtn region1 psaecol numpes
agegr3 where=(subjid ne ""));
by trtn region1 psaecol numpes agegr3 descending n surv subjid;
run;
*--- merge u back to the survival function to find the time which
      corresponds to the new survival estimate - which is always >
      censored one ---;
*--- if there isn't a record at exactly n surv, then we want the latest
      survival estimate prior to that as the survival estimate ---;
PROC SQL;
 CREATE TABLE tte5 as
 SELECT pred1.ttpe, pred1.survival,
       tte4.trtn, tte4.region1, tte.agegr3
        tte4.psaecol, tte4.numpes, tte4.usubjid, tte4.cnsr, tte4.p, tte4.u,
        tte4.n surv, tte4.o ttpe, tte4.o surv
```

CONFIDENTIAL Page 124 of 139

```
FROM tte4 LEFT JOIN pred1
ON pred1.trtn=tte4.trtn AND pred1.region1=tte4.region1 AND
    pred1.psaecol =tte4.psaecol AND pred1.numpes=tte4.numpes AND
    pred1.survival >= tte4.n_surv;

QUIT;

PROC SORT DATA=tte5 (RENAME=(ttpe=pred_ttpe)) OUT=tte6;
    BY trtn region1 psaecol numpes agegr3 usubjid n_surv DESCENDING o_surv;
RUN;

DATA tte7;
    SET tte6;
    BY trtn region1 psaecol numpes agegr3 usubjid n_surv DESCENDING o_surv;
    IF LAST.usubjid THEN OUTPUT;
RUN;

The variable pred_ttpe is the new predicted Time to Pulmonary Exacerbation event.
```

Step 4: Using the original tte dataset, replace any participants censored prior to Week 52 as identified using ttpe and cnsr, with the pred\_ttpe from the above process, updating their censoring flag to be an event. Participants with an imputed event which is less than Day 365 will be considered non-responders. Participants with imputed event which is >= Day 365 will be considered Responders (as we predict they would not have have a PE prior to Week 52 even if they remained on the study). Note: this will create 100 datasets. Each of the datasets will be analyzed using a logistic regression model outputting the parameter estimate and standard error for the trtn (Active vs Placebo) comparison (for example - into pe1 to pe100).

```
PROC LOGISTIC DATA=tte8;
BY _imputation_;
CLASS trtp (ref="Placebo") REGION1(ref="North America")
        numpes (ref=">=3") psaecol (ref="Negative") agegr3 (ref="Adult");
MODEL statusn = trtn region1 numpes psaecol agegr3/CLODDS=WALD ORPVALUE;
ODS OUTPUT PARAMETERESTIMATES=pes COVB=lgscovb;
RUN;
```

CONFIDENTIAL Page 125 of 139

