### **Computations for Step 1:**

Samples from the posterior distribution can be drawn with the BAYES statement in PROC GENMOD based on only the observed data, which applies an iterative algorithm. After a sufficient number of "burn-in" iterations (NBI=200), an appropriate number of samples from the posterior distribution are simulated (NMC=100) and can be saved into a dataset:

CONFIDENTIAL Page 114 of 139

```
*--- Merge posterior samples with observed data ---;

PROC SQL;

CREATE TABLE _40join AS

SELECT *

FROM _16keepTrt, _25bayes

ORDER BY _imputation_, usubjid
;

QUIT;
```

The above statements simulate 100 values of  $\theta_1 = (\beta, c)$  in dataset \_25bayes given the observed data on PEs which can then be used in Step 2 to create 100 imputed datasets. Further,  $\psi_1$  and  $\psi_2$  can be calculated and the dispersion parameter c obtained at the same time.

The values for  $\theta_1$  in row k of \_25bayes are used to impute the missing values in the k-th imputed dataset.

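### SAP Appendix I: the exacerbation-free imputation repeats only the uniform draw and links no separate posterior parameter draw to each dataset, so the pooled standard error for H5/H6 is slightly too small

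*SAP*

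**What the plan says.** SAP 8.3.2.1 treats responder status as missing for participants who leave the study before Week 52 without a confirmed PE. It imputes their first event time, builds 100 datasets, fits a logistic model to each and pools with Rubin's rules. The detail is in Appendix I, in the section on imputing missing event times.

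- **Step 2** fits one Bayesian piecewise exponential model, "outputting the survival estimates for each set of covariates into pred1 dataset". It says that beta-hat "is a vector of model parameters samples from a posterior Bayesian distribution of model parameters estimated from the observed data".
- **Step 3** computes p from the survival curve at the censoring time (b.1), draws u uniformly between p and 1 (b.2), and solves for the event time on the same curve (b.3). It then says that "b.2) will be repeated 100 times creating 100 separate datasets".
- **The code under Step 3** joins the curves to participants on treatment, region, *Pseudomonas* status, prior PEs, age group and time. One line of the join reads "pred1.psaecol =tte.psaecol AND pred1.numpes=tte.numpes AND". The comment on what varies is "use 100 different seeds to ensure reproducibility", and the seed feeds only the uniform draw.

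The Appendix I tipping-point analysis for time to first PE uses the same Step 2 and repeats only b.2 in its Step 3.

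The primary endpoint is handled differently. Appendix I, under multiple imputation assuming MAR, defines the method in two steps: simulate the parameters from their posterior, then simulate the missing data given those parameters. Under Computations for Step 1 it generates 100 posterior samples and says that the values in row k "are used to impute the missing values in the k-th imputed dataset".

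**The concern.** Rubin's rules give a valid variance when each imputed dataset reflects both sources of uncertainty: the random outcome given the model, and the estimation error in the model itself. If all 100 datasets are built from the same curves, only the first source enters the between-imputation variance. The pooled standard error is then too small, and confidence intervals and p-values lean towards significance.

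This matters more for the responder endpoint than it would in a sensitivity analysis, because the imputation is part of the main analysis. H5 and H6 form Family 3 in SAP Table 3, and their p-values enter the gatekeeping algorithm in SAP 6.3.2 and the adjusted p-values in Appendix J.

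**Working it through.** **1. What the text allows.** There are three possible contents for the curve dataset from Step 2.

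- One posterior-averaged curve per covariate set: all 100 imputations share it, and parameter uncertainty is left out.
- One posterior draw: all 100 imputations share that draw, and parameter uncertainty is again left out.
- Many draws: the displayed joins have no key to match draw k to dataset k. They would return several rows per participant, and the last-record step keeps one.

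None of these gives each imputation its own parameter draw.

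**2. Design inputs.** The documents state no standard error, power or dropout rate for the responder endpoint. The nearest stated figure is the 90% power in Protocol 10.1, with 540 per arm, placebo rate 1.2, rate ratio 0.70, dispersion 1 and two-sided alpha 0.005 per comparison.

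- Active rate = 1.2 × 0.70 = 0.84.
- Var(log rate ratio) = (1/1.2 + 1)/540 + (1/0.84 + 1)/540 = 0.00340 + 0.00406 = 0.00745, so SE = 0.0863.
- |ln 0.70|/SE = 0.3567/0.0863 = 4.13. Subtracting 2.81 leaves 1.32, which gives power 90.7%.

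This reproduces the stated 90%. The same inputs imply exacerbation-free proportions of 1/(1 + 1.2) = 45.5% and 1/(1 + 0.84) = 54.3%, and a log odds ratio of ln(1.2/0.84) = 0.357.

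**3. Size of the effect.** This was simulated under those inputs with 1,500 trials per scenario. Events followed a gamma-frailty (negative binomial) process, and one-year dropout of 5% to 30% was assumed. Imputation used an 8-interval piecewise exponential model and 100 imputations. Rubin's rules, T = W + (1 + 1/100)B, were applied to the log odds ratio of one dose against placebo. Posterior draws used a normal approximation.

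| Assumed dropout | Status imputed | SE, only u redrawn | SE, new parameter draw each time | SE too small by | B too small by | Coverage, only u / new draw |
|---|---|---|---|---|---|---|
| 5% | 3.5% | 0.1239 | 0.1239 | 0.02% | 1.5% | 0.954 / 0.955 |
| 10% | 7.1% | 0.1255 | 0.1256 | 0.1% | 4% | 0.937 / 0.937 |
| 15% | 10.7% | 0.1271 | 0.1273 | 0.2% | 6% | 0.951 / 0.951 |
| 20% | 14.2% | 0.1286 | 0.1292 | 0.4% | 8% | 0.959 / 0.958 |
| 30% | 21.5% | 0.1318 | 0.1331 | 1.0% | 12.5% | 0.948 / 0.948 |

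Monte Carlo error of coverage is about 0.6 points. Reusing one posterior draw for all 100 datasets gave SEs of 0.1239 to 0.1319 and coverage of 0.937 to 0.957.

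**4. Why B falls noticeably but the SE hardly moves.** At 20% dropout with proper imputation, 1.01 × B = 1.01 × 0.001692 = 0.00171, and T = 0.12915² = 0.01668. B therefore makes up about 10.2% of T. Losing 8.2% of that share removes 0.082 × 0.102 = 0.84% of the variance, or about 0.42% of the SE. At the design effect, z moves from 0.357/0.12915 = 2.76 to 0.357/0.1286 = 2.78.

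**5. Strata and age group.** The simulation above had treatment only. A second one, with all three arms, the strata and age group, gave SEs too small by about 0.1%, 0.5% and 1.2% at 10%, 20% and 30% dropout.

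**The case against.** The strongest reply is that the plan does describe posterior sampling. Step 2 says so in words, and the program that would make and store the draws is not visible in the text available, so draws by imputation there cannot be ruled out. The displayed code is also schematic. It selects a column from a table that is not in the join, mixes two subject identifiers, uses a placeholder for the seed, and runs the logistic model by an imputation index that no displayed step for this endpoint creates. A missing draw index in such code is weak evidence on its own.

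This reply stands in part. A reader might infer that the SAP plainly rejects posterior sampling for this endpoint. The documents do not support that, and the plan is better called internally unclear. But the point does not rest on the code alone. The Step 3 prose names b.2 as the step that is repeated, while b.1 and b.3 use beta-hat throughout. Describing beta-hat as a posterior sample does not put a different sample into each dataset.

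A second reply is that the effect is negligible. On size this is close to right, as the table shows. A reader might get a larger figure from a simple binary approximation, with W = 1/N and between-imputation variance m²(1/n_mis + 1/n_obs) against m²/n_mis, where m is the fraction missing. The ratio of total variances is then 1 − m², which gives SEs 0.5%, 1.1% and 2.0% too small at 10%, 15% and 20% missing. That treats each missing status as carrying no follow-up. The SAP imputes only participants who leave without a confirmed PE, conditional on the PE-free time already observed, so these figures overstate the effect.

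**Conclusion.** The point holds as a minor specification gap with a known direction. Followed as written, the H5/H6 main analysis pools imputations that share one set of curves, and its standard error is slightly too small: about 0.1% at 10% dropout, 0.4–0.5% at 20% and 1.0–1.2% at 30%. Coverage matched proper imputation to within 0.1 point in the treatment-only simulation. A changed conclusion for H5 or H6 is unlikely.

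These sizes rest on the plan's design rates and on dropout rates that are assumed, since the documents give none. Uncertainty in small cells such as adolescents is somewhat understated in the treatment-only simulation, which is why the upper ends come from the one with strata and age group.

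A reader might extend the point to the confirmatory time-to-first-PE result. That does not follow, because SAP 8.3.1.2 plans no imputation of event times in the H3/H4 main analysis. Only its tipping-point analysis shares the wording. That analysis is a sensitivity analysis, run only if the main result is significant (SAP 6.2), and no size was calculated for it.

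**What to change.** In Appendix I, Step 3 of the responder imputation and Step 3 of the time-to-first-PE tipping point, state that steps b.1 to b.3 are repeated for each imputation k using posterior parameter draw k and a new uniform draw. In Step 2, keep 100 posterior samples and output the curve dataset by draw. Add the imputation index to every merge of the curves with the participant data. This follows the pattern that the SAP already sets for the primary endpoint.

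The cost is minor programming and a few lines of SAP text, with no effect on data collection or on the estimand. If the Step 2 program already stores draws by imputation, only the Step 3 wording and the merge keys need correcting.

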#### PROC SQL;

```
PROC SORT DATA=tte5 (RENAME=(ttpe=pred_ttpe)) OUT=tte6;
BY trtn region1 psaecol numpes agegr3 usubjid n_surv DESCENDING p_surv;
RUN;
```

```
DATA tte7;
   SET tte6;
   BY trtn region1 psaecol numpes agegr3 usubjid n_surv DESCENDING p_surv;
   IF LAST.usubjid THEN OUTPUT;
RUN;
```

The variable pred\_ttpe is the new predicted Time to Pulmonary Exacerbation event.

Step 4: Using the original tte dataset, replace any participants censored prior to Week 52 as identified using ttpe and cnsr, with the pred\_ttpe from the above process, updating their censoring flag to be an event. Note: this will create 100 datasets separately for each delta tipping point. Each of the datasets will be analyzed using a cox proportional hazards model outputting the parameter estimate and standard error for the trtn (Active vs Placebo) comparison (for example - into pe1 to pe100).

CONFIDENTIAL Page 120 of 139

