### Step 5: combine the estimates for the 100 datasets into I PE, and use mianalyze in order to give 1 p-value for the treatment comparison corresponding to each delta value fitted.

Skeleton code for this part may be based on the following.

PROC MIANALYZE PARMS(CLASSVAR=CLASSVAL) = PES;
 CLASS trtp region1 numpes psaecol agegr3
 MODELEFFECTS trtp region1 numpes psaecol agegr3;
 ODS OUTPUT PARAMETERESTIMATES = pes2;
RUN;

CONFIDENTIAL Page 126 of 139

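### The Appendix I code for the exacerbation-free responder analysis does not implement SAP Section 8.3.2.1: the imputed time is picked by a key that is constant within participant, the look-up ignores age group, and the two dose-versus-placebo log odds ratios are never fitted or pooled

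*SAP*

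**What the plan says.** SAP Section 8.3.2.1 specifies a logistic model with treatment, the stratification factors and age group. It asks for an odds ratio and Wald p-value for each dose against placebo. Participants who leave before Week 52 without a PE get imputed first-event times in 100 data sets, combined by Rubin's rules. The section refers to Appendix I for the SAS implementation. The two tests are H5 and H6 in Table 3.

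In Appendix I, the part on imputing missing event times for early discontinuations runs as follows:

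- **Step 1:** "Create a dataset named tte containing 1 row per participant".
- **Step 3, method (b.1 to b.3):** take survival at the censoring time, draw a uniform value above the corresponding failure probability, and impute the time at which the participant's own curve reaches that value.
- **Step 3, code:** the first merge with the curve table `pred1` matches on age group. The later look-up join has "pred1.psaecol =tte4.psaecol AND pred1.numpes=tte4.numpes AND" followed by the requirement that tabulated survival is at least `n_surv`; it has no age-group condition. The result is sorted "BY trtn region1 psaecol numpes agegr3 usubjid n_surv DESCENDING o_surv", and the last row per participant is kept.
- **Step 4:** "Participants with an imputed event which is less than Day 365 will be considered non-responders". The logistic call declares `trtp` as the class variable but prints "MODEL statusn = trtn region1 numpes psaecol agegr3/CLODDS=WALD ORPVALUE". The raw parameter estimates are saved.
- **Step 5:** this is labelled skeleton code and pools "MODELEFFECTS trtp region1 numpes psaecol agegr3".

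The corresponding code for the time-to-first-PE tipping point sorts "BY trtn region1 psaecol numpes agegr3 usubjid n_surv DESCENDING p_surv".

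**The concern.** The look-up exists to find the latest tabulated time whose survival is still at or above the drawn value. That requires ordering the candidate rows by looked-up survival or by time, within the participant's own curve. The printed sort uses neither, and the join does not confine rows to the right curve.

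The model then uses a treatment variable that differs from the one declared in CLASS and from the one pooled. H5 and H6 each concern one dose against placebo, so a single shared slope or a deviation from the arm average answers neither. Both hypotheses are under multiplicity control, and no other text prescribes how rows are selected or how treatment is parameterised in the imputed-data model.

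**Working it through.** The plan gives no figure for this step, so the check is a trace of the printed code plus illustrations.

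**1. Sort key.** `n_surv` is one draw per participant per imputation. `o_surv` is survival at the participant's own censoring time. Both are taken from the participant-side table: "tte4.n surv, tte4.o ttpe, tte4.o surv" (underscores are missing in the available text). With one row per participant in that table, both are constant across all curve rows joined to that participant. The columns that do vary, the looked-up time and `pred1.survival`, are selected but not sorted on. All rows therefore tie, and the one kept is whichever arrives last.

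This was illustrated by a small simulation with assumed exponential curves: hazard 0.0019 per day for adults and 0.0010 for adolescents, censoring between Day 30 and Day 329, age group matched correctly. Each cell gives the share of imputed times before the participant's own censoring time / before Day 365.

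| Ordering | Adults | Adolescents |
|---|---|---|
| Sorted on looked-up survival | 0% / 29.5% | 0% / 17.3% |
| Printed key, rows arrive in ascending time | 0% / 28.9% | 0% / 16.7% |
| Printed key, rows arrive in descending time | 100% / 100% | 100% / 100% |
| Printed key, rows in arbitrary order | 54% / 97% | 51% / 98% |

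**2. Age group.** Under the same assumed curves, with no age match and rows in ascending time, 8.3% of adults' times fall before Day 365 instead of 28.9%. With no age match but a sort on survival, adults barely change (28.9% against 29.5%). Adolescents go from 17.3% to 38.9%, with 7.3% of their times before their own censoring.

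**3. Treatment coefficient.** Inputs from protocol Section 10.1: placebo rate 1.2, dispersion 1, rate ratio 0.70, 540 per arm.

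*Input check.* Variance of the log rate ratio = (1/1.2 + 1)/540 + (1/0.84 + 1)/540 = 0.00745, SE 0.0863. Then z = 0.3567/0.0863 = 4.13, and power at two-sided 0.005 is Φ(4.13 − 2.81) = 90.7%, in line with the stated 90%.

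*Target.* P(no PE) = 1/(1 + mean): 1/2.2 = 0.455 on placebo and 1/1.84 = 0.543 on a dose. Odds ratio = 1.2/0.84 = 1.429, log 0.357. SE = √[1/(540 × 0.543 × 0.457) + 1/(540 × 0.455 × 0.545)] = 0.122, z = 2.92.

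*As printed.* The tipping-point data set codes `trtn` as 1 = 25 mg, 2 = 10 mg, 3 = placebo; the responder Step 1 list shows only `trtp`. With near-equal arms, the slope on a 1-2-3 score is (θ_placebo − θ_25)/2, where θ is an arm's log odds. The 10 mg arm drops out.

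- Both doses effective: −0.357/2 = −0.178 per unit (exp 0.837).
- Only 25 mg effective: −0.178 again, z −2.92.
- Only 10 mg effective: 0.

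One number cannot test H5 and H6 separately.

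*If `trtn` is merely replaced by `trtp`.* No parameterisation option is printed, and PROC LOGISTIC defaults to effect coding (a software fact, not stated in the documents). Each dose parameter is then θ_dose minus the mean of the three arms. For a common log odds ratio L and per-arm variance v:

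- estimate L/3, variance 2v/3, against L and 2v for the contrast with placebo;
- z ratio = (1/3)/√(1/3) = 0.577.

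Here L/3 = 0.119 (exp 1.126) and z is about 0.577 × 2.92 = 1.69. Power at nominal two-sided 0.05 falls from 83% to 39%. If one dose has no effect, its parameter is −L/3 = −0.119 (exp 0.888). With an odds ratio of 1.40 for the effective dose, the corresponding values are exp(0.336/3) = 1.12 under equal effects and exp(−0.336/3) = 0.89 for a null dose.

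**4. Whether the code runs.** The sort of `tte4` keeps a short variable list in place, dropping `o_surv` and others needed next. It filters on `subjid`, not `usubjid`. The following query selects `tte.agegr3`, although `tte` is not among its source tables. Step 5 requests an effect that Step 4 did not fit.

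**The case against.** The strongest reply is that the specification is sound and only the code is not. Section 8.3.2.1 names the right odds ratios, b.1 to b.3 describe the imputation correctly, and a code comment says which survival row is wanted. Step 4's text speaks of active versus placebo, and Step 5 is only a skeleton. An earlier Appendix I block also requests pairwise odds ratios. This stands: it is a conflict between code and text, not a wrong choice of analysis. It does not settle the matter, because Steps 3 and 4 are not labelled skeleton code and the earlier block's odds ratios are not what Steps 4 and 5 save and pool.

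A reader might infer more than the documents support:

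- *That the kept row is always wrong.* It is order-dependent. If the curve rows stay in ascending time within the right curve, the intended row survives.
- *That no dropout can ever be imputed to Day 365 and so count as a responder.* This turns on which times `pred1` holds, and the code that creates it is not in the available text. Follow-up also runs to the actual Week 52 visit, which has a ±7-day window.
- *That the reported p-value will test the wrong hypothesis.* The code would probably stop first and would have to be repaired.

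The contrast with `p_surv` shows only that the two sorts differ, since the statement defining `p_surv` is not readable in the available text. Section 8.3.2.1 also allows age group to be dropped for estimability, which would remove the second fault.

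**Conclusion.** The point holds as a conflict between the Appendix I code and the SAP's own text, in three respects: the row-selection key, the missing age-group match, and the treatment parameterisation. The third matters most, because the obvious one-word repair still pools the wrong quantity.

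The size depends on the repair. As printed, one slope serves both doses. With `trtp` under default coding, the estimate is one third of the log odds ratio and z is 58% of its correct value when the doses are equally effective. These figures assume near-equal arms; the power figures also assume the design rates and a full year of follow-up. The look-up percentages rest on assumed curves and show direction only.

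The documents give no rate of early discontinuation without a PE. At an assumed 10% to 15%, 540 × 0.10 = 54 to 540 × 0.15 = 81 participants per arm would be classified through the look-up. That is the number exposed to the fault, not the number misclassified.

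**What to change.** - **Join:** add `agegr3` to the look-up condition. In the preceding step, reset the retained survival at the first row of each age group; it is now reset at `numpes`.
- **Row selection:** sort by descending `pred1.survival` within participant and keep the last row. More simply, classify a dropout as a responder when `n_surv` is below that participant's predicted survival at Week 52. The imputed time lies beyond Week 52 exactly when the drawn survival is lower than survival there, so no tabulated time is needed.
- **Model:** use `CLASS trtp(REF='Placebo') / PARAM=REF` with `MODEL statusn(EVENT='1') = trtp ...` and the same covariates.
- **Pooling:** combine the two dose-versus-placebo log odds ratios by Rubin's rules, one for H5 and one for H6.
- **Clean-up:** correct the kept-variable list, the participant identifier and the table reference, then run the block on dummy data. Confirm that every imputed time follows the participant's own censoring time.

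The cost is a few lines of code and a short SAP correction before unblinding. No new data are needed.
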